6 ANALYSIS POPULATION

Analyses for the safety and efficacy endpoints will be performed using the intent-to-treat (ITT) population. The ITT population will consist of all subjects randomized in the study and will analyzed in the group to which they were randomized regardless of the treatment actually received.

Supportive analyses for the safety and efficacy endpoints will be performed on the astreated (AT) population and the per-protocol (PP) population. The AT population will consist of all randomized subjects, but they will be analyzed according to what device/treatment they actually received. The PP population is a subset of the ITT population consisting of subjects that do not have any major protocol deviation that might affect the measurement of the primary endpoints. Subjects randomized to the MYNX CONTROL[™] Venous VCD that do not receive the device due to device malfunction and are subsequently treated with manual compression, will remain part of the ITT analysis population. These subjects will also be part of the AT analysis population and analyzed in the manual compression group. They will not be part of the PP analysis population.

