16.2 Device Failures and Malfunctions

A device malfunction is considered a failure of a device to meet any of its performance specifications or otherwise perform as intended. Performance specifications include all claims made in the IFU/Clinical Protocol.

If a product malfunction occurs, the site must notify within 24 hours or one working day the Sponsor and/or enter details of the complication and its management in the respective CRF. If applicable, the malfunctioned product and any other materials used during the index procedure should be returned according to the Sponsor's instructions.

If a product malfunction occurs, detailed information on the product, circumstances of the malfunction as well as any complications and their management will be collected and reported.

Any patients randomized to the device arm who do not receive the MYNX CONTROL[™] Venous VCD due to device malfunction would be treated with (converted to) manual compression, or much less likely – surgery – to close the access site. All device failure patients should be followed to 30 days and have a visual assessment of the access site(s) at that time. Such visual assessments are particularly important since patients experiencing device failures are more likely to have access site-related complications, and a complete and accurate evaluation of these patients is important to help ensure a rigorous IDE study.

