 $S_{j(i)} \sim N(0, \sigma_S^2)$

and

 $e_{k(ij)} \sim N(0, \sigma_e^2)$

To adjust for the correlation in hemostasis time between the access sites within subject it is assumed that the correlation structure is compound symmetric. A sample size of 150 subjects (100 MYNX CONTROL[™] VCD and 50 manual compression) will provide approximately 95% power to detect a difference in hemostasis times of 7 minutes between MYNX CONTROL[™] VCD and manual compression. Note that these calculations were made in the log transformed space to assess power. Also, the variation between access sites within subject was estimated at approximately half of the variation observed between subjects.

Major Complication Rate:

The rate of combined major venous access site closure-related complications through 30 days post procedure, attributed directly to VCD or manual compression without other likely cause is the primary safety endpoint. The one-sided Type I error was set to 0.025 for the purpose of sample size calculation. The safety endpoint will be analyzed using a non-inferiority approach on a per limb basis. For the purposes of sample size

calculation, both groups are assumed to have a 1.5% major complication rate. The non-inferiority window has been established at 5 percentage points.

Within-subject correlation can affect the power of the study depending on the degree of correlation. However, the degree of correlation within-subject due to potentially multiple limbs is unknown and there is not robust and relevant data on which to base any associated assumption. Since this is unknown, conservatively sample size is calculated assuming only one limb per subject, or in other words, the number of subjects in the study assuming independence between subjects. Calculations for a two-sample test of binomial proportions for a Z test under a normal approximation show a sample size of 204 subjects should provide approximately 80% power for this endpoint. To the extent that some subjects will contribute multiple limbs to the actual analysis, the power would be higher than that from calculations based only on the numbers of independent subjects. Though missing data for the primary safety endpoint is unlikely, the additional data contributed by multiple limbs will help offset any power loss due to missing data.

Time to Discharge Eligibility (secondary endpoint):

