8.4 Analyses of Safety Endpoints

8.4.1 Primary Safety Endpoint Analysis

The primary safety endpoint analysis will be performed on a per limb basis. The null and alternative hypotheses of the primary safety comparison are given below:

Ho: $P_{Mynx \ Control} - P_{manual \ compression} \ge \delta$ Ha: $P_{Mynx \ Control} - P_{manual \ compression} < \delta$

where P_X is the proportion of limbs experiencing a major venous access site closurerelated complications through 30 days post-procedure and δ is the non-inferiority window. For this analysis, δ is set at 5 percentage points.

This endpoint will be analyzed using a GEE approach for a logistic regression model with a compound symmetric working covariance structure where occurrence of an AE is the binary response variable and treatment group is the only explanatory variable. Least square means for each treatment group will be calculated along with a two-sided 95% confidence interval. The one-sided 97.5% confidence bound (equivalent to the appropriate bound from the two-sided 95% interval) will be compared to the non-inferiority window. If the upper bound is less than the non-inferiority window, then the two treatment groups will be considered non-inferior relative to the proportion of limbs experiencing a major venous access site closure-related complication.

As a supplementary analysis, a generalized linear mixed model will be used where subject will be entered into the model as a random effect and a compound symmetric correlation structure applied those subjects contributing two limbs.

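### Subjects who miss the device through malfunction count as manual compression in AT and are dropped from PP, so both supportive safety analyses lean toward the device if those subjects have excess major complications

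*SAP*

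**What the plan says.** SAP 6 makes ITT the main set: "Analyses for the safety and efficacy endpoints will be performed using the intent-to-treat (ITT) population". AT and PP are supportive, for safety and efficacy alike. The general AT rule is "The AT population will consist of all randomized subjects, but they will be analyzed according to what device/treatment they actually received". PP is the part of ITT without a major protocol deviation that could affect measurement of the primary endpoints.

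SAP 6 then adds a specific rule for subjects randomized to the device who do not receive it because it malfunctioned and who are then compressed. They stay in the device arm for ITT. For AT, "These subjects will also be part of the AT analysis population and analyzed in the manual compression group". For PP, "They will not be part of the PP analysis population". Protocol 16.3 gives the same general AT and PP definitions without the malfunction rule.

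Protocol 16.2 says that such patients "would be treated with (converted to) manual compression, or much less likely" surgery. It asks for 30-day follow-up with visual assessment of the sites, because "patients experiencing device failures are more likely to have access site-related complications".

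**The concern.** The primary safety test is a non-inferiority test (SAP 8.4.1: "For this analysis, δ is set at 5 percentage points"). In such a test AT and PP are the natural cross-check on ITT. A cross-check is useful only if it does not lean the same way as the result that it is meant to challenge.

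Here a subset that the protocol itself expects to do worse leaves the device arm in both supportive sets. In AT its events are added to the comparator. In PP they disappear. An event adjudicated as caused by the device, in a subject later compressed, would then count against manual compression in AT.

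The PP exclusion also sits badly with its own criterion. Protocol 17.5.2 defines a deviation as a departure from an element of the protocol, with missed assessments, out-of-window visits and eligibility violations as examples. A malfunction is a product failure, and conversion to compression is the path that Protocol 16.2 describes.

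**Working it through.** **Inputs from the documents.** 136 device and 68 manual compression subjects. For major complications, "both groups are assumed to have a 1.5% major complication rate" (SAP 5). Margin 5 points, one-sided alpha 0.025. Time to ambulation (TTA) means 3 h and 6 h. Time to hemostasis (TTH) means 6 min and 13 min.

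**Assumed, because the documents give no figure.** The number of malfunction non-receivers, k = 3, 7 or 14, and their major-complication risk, r = 5%, 15% or 25%. All other subjects are at 1.5%. The calculation is per subject, whereas the endpoint is per limb.

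**The plan's own figure first.** The standard error is sqrt(0.015 × 0.985 × (1/68 + 1/136)) = 0.01805. Power is Φ(0.05/0.01805 − 1.96) = 79.1%, which matches the stated 80% or so. This figure does not depend on the AT or PP rule.

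**Safety, expected differences (device minus compression).**

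- ITT = [(136 − k) × 0.015 + k × r]/136 − 0.015 = k(r − 0.015)/136
- AT = 0.015 − [68 × 0.015 + k × r]/(68 + k) = −k(r − 0.015)/(68 + k)
- PP = 0.015 − 0.015 = 0

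| k, r | ITT | AT | PP | ITT-to-AT swing | ITT-to-PP shift |
|---|---|---|---|---|---|
| 3, 5% | +0.08 | −0.15 | 0 | 0.2 | 0.1 |
| 7, 15% | +0.69 | −1.26 | 0 | 2.0 | 0.7 |
| 14, 25% | +2.42 | −4.01 | 0 | 6.4 | 2.4 |

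Values are percentage points. For the middle row, ITT = 7 × 0.135/136 = 0.0069 and AT = −7 × 0.135/75 = −0.0126. If r = 1.5%, all three differences are 0.

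**Can the conclusion differ between sets?** Take assumed counts: 7 non-receivers with 2 events, 2 events in the other 129 device subjects, and 1 event in 68 controls. The upper bound is the difference + 1.96 × unpooled standard error, a simple stand-in for the planned GEE.

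- ITT, 4/136 vs 1/68: difference +1.47, bound 5.50, misses the margin.
- AT, 2/129 vs 3/75: difference −2.45, bound 2.47, meets it.
- PP, 2/129 vs 1/68: difference +0.08, bound 3.65, meets it.

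This shows only that a split is possible. Two events in 7 is 29%, just above the assumed range.

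**Time endpoints.** Let f be the converted share of the device arm, k = 136f, and t the mean time of converted subjects. For TTH, f is treated as a share of sites, with equal numbers of sites per subject.

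- TTA: ITT = 3(1 − f) + tf − 6; AT = 3 − (68 × 6 + kt)/(68 + k); PP = −3.
- Setting ITT = AT gives t = [6 + 3f − 408/(68 + k)]/[f + k/(68 + k)]. For f = 2%, 5% and 10% this is 4.97, 4.94 and 4.88 h.
- The same step for TTH gives t = [13 + 6f − 884/(68 + k)]/[f + k/(68 + k)], or 10.61, 10.52 and 10.38 min.

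Above these times AT favors the device relative to ITT; below them it goes against it. With converted subjects at the compression means and f = 5% to 10%, TTA is −2.85 to −2.70 h in ITT and −3.00 h in AT and PP. The TTH benefit is 6.65 to 6.30 min in ITT and 7.00 min in AT and PP. With 7 converted subjects walking at an assumed 2.5 h, ITT is −3.03 h, AT is −2.67 h and PP is −3.00 h.

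**The case against.** The strongest reply is that nothing decisive is touched. ITT is primary and keeps these subjects in the device arm, trial success (Protocol 16.9.1) is not tied to AT or PP, malfunctions and their complications must be collected and reported, and device success is analyzed separately. Analysis by treatment received and exclusion of non-receivers from PP are common conventions, and the SAP states both in advance. All of this stands. It makes the matter one of supportive evidence, and redefining the sets is partly a preference.

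The inputs can also be challenged. Protocol 16.2 speaks of access-site complications in general, and the minor ones include ecchymosis. The documents give neither a malfunction rate nor a 15% to 25% major-complication risk. That stands too: the direction is conditional on excess major complications, and the size is illustrative.

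Three stronger readings are tempting and are not supported.

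- A reader might infer that both sets favor the device on every endpoint. For TTA and TTH in AT the direction depends on the break-even times. Protocol 14.2 requires the device group to attempt ambulation within 2 to 2.5 h and does not say whether converted subjects are exempt, so AT could move against the device.
- A reader might infer that long hemostasis times are charged to compression. No document gives a time for converted sites. At the compression mean of 13 min the AT control mean does not change, and the gain comes from slow sites leaving the device arm.
- A reader might infer that every device failure is reassigned. The rule covers only subjects who do not receive the device. A subject who received it without reaching hemostasis falls outside that sentence.

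Nor would it be right to say that the supportive sets give no reassurance at all. With no such malfunctions the effect is zero, and PP still tests the influence of other major deviations.

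**Conclusion.** The point holds for safety, on one condition. If malfunction non-receivers have more major complications than other subjects, AT and PP both move toward the device relative to ITT, and their agreement with ITT is weak corroboration of non-inferiority. The primary analysis, the sample size and the success rule are unaffected.

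The size cannot be known from the documents. Under the assumed 3 to 14 malfunctions at 5% to 25% risk, the ITT-to-AT swing is 0.2 to 6.4 points against a 5-point margin, and PP returns to about 0. For TTA and TTH, AT favors the device only if converted subjects average more than about 4.9 to 5.0 h or 10.4 to 10.6 min. PP favors it only if they are slower than device successes.

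**What to change.** In SAP 6:

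- For the supportive safety analysis, keep every subject in whom the study device was introduced in the device group. Either define AT by the first closure method attempted, or leave the current AT as it is and add this set beside it.
- Keep malfunction subjects in PP unless they have a separate major protocol deviation, or report PP with and without them.
- Tabulate the outcomes of malfunction subjects separately.
- In the same edit, say how AT classifies a subject with several access sites when only some devices fail. The present rule does not cover that case.

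The cost is SAP wording and a little extra analysis. The sponsor's downside is that supportive device results may look slightly less favorable.

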7 RANDOMIZATION

This is a randomized, controlled, open label study. Before the first subject is enrolled in the study, a randomization schedule will be generated by the study statistician and uploaded into an electronic database that can be accessed via computer. The schedule will be generated using a permuted block approach. Randomization will be performed at the conclusion of the index procedure, while the subject is on the table and the operator is able to visualize all access sites to verify eligibility. Since one of the primary endpoints of this study is time to ambulation, randomization will be done at the subject level to avoid the possibility of a subject receiving both MYNX CONTROL[™] Venous VCD and manual compression. Randomization will be stratified by study center with a 2:1 randomization ratio for MYNX CONTROL[™] Venous VCD vs. manual compression for access site closure.

Roll-in patients will not be randomized. All roll-in subjects will receive the MYNX CONTROL[™] Venous VCD.

8 STATISTICAL METHODS OF ANALYSIS

8.1 General Considerations

All statistical programming will be performed using SAS[®] version 9.4 or above, or other widely accepted statistical or graphical software.

Summary tables will be based only on all available data. For categorical variables, the numerator, denominator, rate (%), and exact 95% CI will be calculated. For continuous variables, the median, mean, standard deviation, interquartile range, number of observations, minimum and maximum values, and 95% CI, as appropriate, will be presented. For each parameter, the baseline value will be defined as the last non-missing value collected at the time closest to but before treatment with the investigational device.

All statistical tests will be performed at the two-sided 0.05 significance level, unless otherwise specified.

The analyses described in this section assume that 204 subjects have been enrolled and 30-day follow-up complete, and that 72 of those subjects have been consented to the DUS sub-study. If the sub-study has not completed enrollment by the time 204 subjects are enrolled in the main study, the analyses described below, with the exception of the DUS sub-study, will be completed on the full 204 subjects and study results will be declared as planned .This will be considered the primary analysis.

Statistical Analysis Plan 31Mar2023

Enrollment will continue until 72 subjects are consented to the DUS sub-study. Once follow-up in the sub-study is complete, all analyses will be re-run on the full complement of subjects enrolled and that analysis will be considered as a supplemental dataset. This plan ensures the statistical methodology for the primary analysis remains unaltered.

8.2 Subject Disposition

Subject accountability will be summarized in tabular form.

8.3 Subject Demographics and Baseline Variables

All baseline variables will be summarized using descriptive statistics. Continuous variable will be summarized using the mean, standard deviation, N, and range. Categorical variable will be summarized as frequencies and proportions. Baseline variables for the two subject groups will be summarized separately

8.4 Analyses of Safety Endpoints

8.4.1 Primary Safety Endpoint Analysis

The primary safety endpoint analysis will be performed on a per limb basis. The null and alternative hypotheses of the primary safety comparison are given below:

Ho: $P_{Mynx \ Control} - P_{manual \ compression} \ge \delta$ Ha: $P_{Mynx \ Control} - P_{manual \ compression} < \delta$

where P_X is the proportion of limbs experiencing a major venous access site closurerelated complications through 30 days post-procedure and δ is the non-inferiority window. For this analysis, δ is set at 5 percentage points.

This endpoint will be analyzed using a GEE approach for a logistic regression model with a compound symmetric working covariance structure where occurrence of an AE is the binary response variable and treatment group is the only explanatory variable. Least square means for each treatment group will be calculated along with a two-sided 95% confidence interval. The one-sided 97.5% confidence bound (equivalent to the appropriate bound from the two-sided 95% interval) will be compared to the non-inferiority window. If the upper bound is less than the non-inferiority window, then the two treatment groups will be considered non-inferior relative to the proportion of limbs experiencing a major venous access site closure-related complication.

As a supplementary analysis, a generalized linear mixed model will be used where subject will be entered into the model as a random effect and a compound symmetric correlation structure applied those subjects contributing two limbs.

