16.9.1 Primary Analysis

Efficacy

The primary efficacy endpoints will be analyzed separately.

The average time to ambulation in each treatment group will be compared using a standard T-test.

The average time to hemostasis will be compared to the treatment groups using a generalized linear mixed model where subject is considered a random effect with multiple access sites. The times to hemostasis in the manual compression group will be reduced by 5 minutes to account for the hypothesis that the time to hemostasis for the MYNX CONTROL[™] Venous VCD is at least 5 minutes less than manual compression. The analysis will consist of testing the coefficient on the fixed effect for treatment group. If that coefficient is found to be significantly different from zero, then the direction will be evaluated to assure that the hemostasis time is reduced on average when using MYNX CONTROL [™] Venous VCD.

Safety

The safety analysis will be completed on a per-limb basis.

This endpoint will be analyzed using a GEE approach for a logistic regression model with a compound symmetric working covariance structure where occurrence of an AE is the binary response variable and treatment group is the only explanatory variable. Least square means for each treatment group and the risk difference between groups will be calculated along with the two-sided 95% confidence interval. The one-sided 97.5% confidence bound (equivalent to the appropriate bound from the two-sided 95% interval) will be compared to the non-inferiority window. If the upper bound is less than the non-inferiority window, then the two treatment groups will be considered non-inferior relative to the proportion of limbs experiencing a major venous access site closure-related complication.

As a supplementary analysis, a generalized linear mixed model will be used where subject will be entered into the model as a random effect and a compound symmetric correlation structure applied to those subjects contributing two limbs.

Version: 3.0 / 31Jan2023

Trial Success

This trial will be considered a success if both primary efficacy endpoints and the primary safety endpoint are achieved.

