8.8 Analysis of Roll-in Subjects

Roll-in subjects will be summarized using descriptive statistics. No formal hypothesis testing will be done on this group.

Time to ambulation will summarized using the mean, median, standard deviation, sample size, minimum, and maximum. A 95% confidence interval for the average time to hemostasis will be calculated using the T-distribution.

Time to hemostasis will first be summarized across access sites within each subject by calculating the mean time to hemostasis by averaging the individual site-specific times. Time to hemostasis will then be summarized across subjects by calculating the mean, median, standard deviation, sample size, minimum, and maximum. A 95% confidence interval for the average time to hemostasis will be calculated using the T-distribution.

The proportion of roll-in subjects experiencing a major access related complication will be calculated along with a 95% confidence interval constructed using the Clopper-Pearson method.

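### Primary safety is decided on a logistic GEE bound whose construction is not stated and which has no rule for an arm without events, yet at the plan's 1.5% rate the control arm has none in 13% to 36% of trials

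*SAP*

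**What the plan says.** Both documents analyse primary safety per limb. SAP 8.4.1 states the hypothesis as device minus control proportion against a margin of 5 points, and the model as follows: "This endpoint will be analyzed using a GEE approach for a logistic regression model with a compound symmetric working covariance structure". Treatment is the only covariate. The SAP gives a 95% interval for each group's least-squares mean and then compares a one-sided 97.5% upper bound with the margin, without saying what quantity is bounded. Protocol 16.9.1 is fuller: "Least square means for each treatment group and the risk difference between groups will be calculated along with the two-sided 95% confidence interval". It does not say how that interval is derived from the logit model.

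The endpoint decides the trial. Protocol 16.9.1: "This trial will be considered a success if both primary efficacy endpoints and the primary safety endpoint are achieved".

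For sizing, SAP section 5 says "both groups are assumed to have a 1.5% major complication rate", that "conservatively sample size is calculated assuming only one limb per subject", and that calculations for a "Z test under a normal approximation show a sample size of 204 subjects should provide approximately 80% power for this endpoint". Protocol 16.8 and SAP section 5 call the within-subject correlation unknown. The share of two-limb subjects is not given.

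Exact intervals appear elsewhere. SAP 8.1: "For categorical variables, the numerator, denominator, rate (%), and exact 95% CI will be calculated". SAP 8.8, on the proportion of roll-in subjects: "experiencing a major access related complication will be calculated along with a 95% confidence interval constructed using the Clopper-Pearson method". Both concern single-group rates. I found no rule in either document for an arm without events or for a model that does not converge.

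**The concern.** At a 1.5% rate the sizing implies about one control event (68 × 0.015 = 1.02) and two device events (136 × 0.015 = 2.04). If the control arm has none, its log-odds has no finite estimate. Software may still print a number, and a Wald-type bound then gives that arm no variance, which favours the device. A score-type bound does not do this.

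So a result well within the plan's expectations could pass or fail according to a method chosen after the counts are known, in an open-label trial. The backup analyses do not help. The supplementary mixed model and the SAP section 11 safety tipping point also work on the logit scale, which is undefined at zero events.

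**Working it through.** **Inputs.** 136 device and 68 control subjects (Protocol synopsis); 1.5% in both arms, margin 5 points, one-sided 0.025, one limb per subject (SAP section 5). Limb counts above 136:68 are assumptions and treat limbs as independent. Results are written as device events v control events.

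**1. The plan's power.** SE = √[0.015 × 0.985 × (1/136 + 1/68)] = 0.01805. Power = Φ(0.05/0.01805 − 1.96) = 79.1%. The stated figure of about 80% reproduces as a Z-formula result.

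**2. Control arm without events.** One limb per subject: 0.985^68 = 35.8%. An average of 1.5 independent limbs: 0.985^102 = 21.4%. Two independent limbs: 0.985^136 = 12.8%. Positive correlation or fewer two-limb subjects moves the figure towards 36%. For control rates from 1% to 3% the range is 50% to 13% at one limb and 25% to 2% at two.

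**3. Does the method change the decision at 136:68?** The Wald bound is d + 1.96 × SE.

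- 2v0: 0.01471 + 1.96 × √(0.01471 × 0.98529/136) = 3.5%. Pass.
- 3v0: 0.02206 + 1.96 × √(0.02206 × 0.97794/136) = 4.7%. Pass.

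The Farrington-Manning test takes its variance under the 5-point null. With no control events here, the restricted control rate is 0 and the SE is √(0.05 × 0.95/136) = 0.01869.

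- 2v0: z = (0.01471 − 0.05)/0.01869 = −1.89, short of −1.96. Fail (bound 5.2%).
- 3v0: z = (0.02206 − 0.05)/0.01869 = −1.50. Fail (bound 6.3%).

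Their probabilities at 1.5% are 0.0975 and 0.0663, together 16.4% of trials. With no control events, 0v0 and 1v0 pass by both formulas, and 4v0 and above fail by both.

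One further result, 3v1 (probability 6.9%), also divides the methods: Wald 4.5%, Farrington-Manning 5.07%, Newcombe 4.99%. Neither arm is empty there, so a zero-event rule does not affect it. The total is 16.4% + 6.9% = 23.3%.

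**4. Sensitivity to limb count.** Exact binomial enumeration at 1.5% in both arms (error: 6.5% v 1.5%). The rule is Farrington-Manning if either arm has no events, and Wald otherwise. No clustering allowance is applied.

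| Limbs | Control arm empty | Wald passes, score fails | Wald error | Error under rule | Power under rule |
|---|---|---|---|---|---|
| 136:68 | 36% | 23% | 3.16% | 2.47% | 71% |
| 142:71 | 34% | 7% | 3.05% | 2.67% | 80% |
| 170:85 | 28% | 10% | 2.82% | 2.50% | 82% |
| 204:102 | 21% | 4% | 2.56% | 2.45% | 94% |
| 272:136 | 13% | 2% | 2.53% | 2.45% | 98% |

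The fall from 23% to 7% takes nine extra limbs in the whole trial. At 142:71 the score bound for 2v0 is 4.99%, so it passes by both methods. The pattern between rows is not smooth: intermediate counts gave Wald error up to 3.3% (140:70) and error under the rule up to 2.8% (150:75).

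**5. Other control rates at 136:68.** Wald error is 5.8% at 0.5%, 2.5% at 2% and 1.8% at 3%.

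**6. A trial fit.** In statsmodels, an exchangeable logistic GEE with 2v0 at one limb per subject gave a control intercept near −26 with a robust SE near zero. With two limbs per subject the intercept was near −28 and the SE undefined. Both fits were flagged as converged.

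**The case against.** Much of the case on the other side stands.

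- **The interval is not absent.** A reader might infer that the plan never asks for a risk-difference interval. Protocol 16.9.1 does, and SAP 8.4.1 states its hypothesis on that scale. What is missing is the construction and the zero-event rule.
- **The 23% is not an established disagreement rate.** It holds only if no subject contributes a second limb, which the plan uses as a conservative sizing device and does not expect.
- **Nor is the trial shown to be underpowered.** If the score bound alone decided every case, power would be 65% at 136:68, but it is 80% at 142:71. Part of the shortfall is discreteness at one exact limb count.
- **Error is not badly inflated.** At the planned rate it is 3.2% for Wald at 136:68. The 5.8% needs a control rate one third of the plan's, and at 3% Wald is conservative.
- **The GEE need not be replaced.** A reader might prefer a score bound with a fixed working correlation such as 0.5 throughout. The plan says it has no robust data on that correlation, so the value has no source in the documents, and the trade-off is debatable.
- **The method is assumed.** The plan names SAS (or other accepted software), and SAS output was not checked. Nor can one say that 0v0 passes under the plan's own model, which then has no finite estimate in either arm. It passes under the Wald and score formulas.

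None of this supplies a rule for an arm without events.

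**Conclusion.** The concern holds as a gap in specification that affects a likely outcome. A success-critical decision has no defined method when an arm has no events. At the plan's own rate the control arm is empty in 36% of trials at one limb per subject and in 13% at two independent limbs. At 136:68, two results covering about 16% of trials then pass or fail according to the unnamed method. That share falls as second limbs are added, to about 2% at 204:102 and 1% at 272:136.

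This rests on the 1.5% rate, on independent limbs, and on Wald as the assumed reading of the unnamed interval. The limb mix and the correlation cannot be settled from the documents. The stated power is correct arithmetic for a Z test, but it is not the power of a fully specified decision rule.

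**What to change.** Before event counts by arm are known, amend SAP 8.4.1 and Protocol 16.9.1 as follows.

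1. Keep the compound-symmetric GEE as the primary analysis. Write the risk difference into SAP 8.4.1 to match the Protocol, and name how its interval is obtained from the model.
2. Add a rule: if either arm has no events, or the GEE does not converge, the decision uses one named score-type one-sided 97.5% upper bound for the risk difference, for example Farrington-Manning, against 5 points. Trigger it on event counts as well as on convergence, because a fit can be flagged as converged with an empty arm.
3. State in advance a conservative allowance for two-limb subjects within that rule. For example, reduce each arm's limb count N to N²/(one-limb subjects + 2 × two-limb subjects × (1 + ICC)) with ICC = 1, and use smaller ICCs as sensitivity analyses.
4. Apply the same rule to the supplementary mixed model. In SAP section 11, when the logit is undefined, run the tipping point by adding events to device limbs with missing status.
5. Replace the single 80% figure by power under this rule over a range of limb mixes. The table's figures (71%, 80%, 82% and 94% at 136:68, 142:71, 170:85 and 204:102) are a starting point. They treat limbs as independent, so they should be recomputed with the allowance in item 3.

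The cost is wording and a recalculation, with no new data and no change of margin or estimand. The downside is lower stated power if few subjects contribute two limbs. The rule also leaves results such as 3v1 to whichever interval item 1 names.
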